3.2 Justification for Study Design

A parallel study design was chosen due to the length of the exposure period. The continue-smoking arm is included as a control group to account for natural variations in responses associated with participation in a long-term clinical trial.

Subjects randomized to receive a *my*bluTM product will be assigned to an e-liquid flavor based upon their preference established during the acclimation period and may be allowed to switch flavors after a period of approximately 28 days. This method was chosen to emulate a natural condition whereby consumers initially experiment with e-liquid flavors in the market before selecting a product for long-term use, and then have the option to switch among other flavors and nicotine strengths in the market as their needs change.

A previous study demonstrated that switching to an early version of the blu product resulted in decreases in BoEs in as few as 5 days (O'Connell et al. 2016). The current study will be primarily conducted in a less-controlled ambulatory environment over a longer period of time to determine whether reductions can be maintained when subjects have access to combustible cigarettes. A longer assessment period also provides for a more comprehensive assessment of subjective effects and impressions of the study products.

4. STUDY POPULATION

Subjects selected for this study will be identified via standard recruitment methods.

4.1 Inclusion Criteria

Subjects must fulfill all of the following inclusion criteria to be eligible for participation in the study.

- 1. Healthy, adult, male or female smoker, 21 to 65 years of age, inclusive, at Screening.
- 2. Reports smoking an average of 5 or more machine-manufactured non-menthol or menthol combustible CPD for at least 1 year prior to Screening. Brief periods of non-smoking (e.g., up to ~7 consecutive days due to illness, trying to quit, participation in a study where smoking was prohibited) during that time will be permitted at the discretion of the Investigator.
- 3. Has a positive urine cotinine test (approximately 200 ng/mL using NicAlert, Accutest Urine Cotinine Test, or other test that provides a similar level of sensitivity, the same type of kit will be used at each site) at Screening and check-in for Test Visit 1.
- 4. Has an exhaled CO > 10 ppm at Screening and check-in for Test Visit 1.
- 5. A female subject of childbearing potential must have been using 1 of the following forms of contraception and agree to continue using it through completion of the study:
 - hormonal (e.g., oral, vaginal ring, transdermal patch, implant, or injection) consistently for at least 3 months prior to check-in for Test Visit 1;

- double barrier method (e.g., condom with spermicide, diaphragm with spermicide) consistently for at least 14 days prior to check-in for Test Visit 1;
- intrauterine device for at least 3 months prior to check-in for Test Visit 1;
- a partner who has been vasectomized for at least 6 months prior to check-in for Test Visit 1;
- abstinence for at least 14 days prior to check-in for Test Visit 1 through discharge from the study.
- 6. A female subject of non-childbearing potential must have undergone one of the following sterilization procedures at least 6 months prior to check-in for Test Visit 1:
 - hysteroscopic sterilization;
 - bilateral tubal ligation or bilateral salpingectomy;
 - hysterectomy;
 - bilateral oophorectomy;

Or be postmenopausal with amenorrhea for at least 1 year prior to check-in for Test Visit 1 and follicle-stimulating hormone (FSH) level consistent with postmenopausal status.

- 7. Is willing to comply with the requirements of the study, including a willingness to use alternative tobacco products as required by the protocol.
- 8. Has daily access to text messaging capable cellular phone for daily product use reporting.
- 9. Provides voluntary consent to participate in this study documented on the signed informed consent form (ICF).

4.2 Exclusion Criteria

Subjects may be excluded from the study if there is evidence of any of the following criteria during Screening or check-in for Test Visit 1, as applicable.

- 1. Has a history or presence of clinically significant gastrointestinal, renal, hepatic, neurologic, hematologic, endocrine, oncologic, urologic, pulmonary (especially bronchospastic diseases and asthma), immunologic, psychiatric, or cardiovascular disease, or any other condition that, in the opinion of the Investigator, would jeopardize the safety of the subject or impact the validity of the study results.
- 2. Has a clinically significant abnormal finding on the physical examination, medical history, vital signs, ECG, or clinical laboratory results, in the opinion of the Investigator.
- 3. Has a positive test for human immunodeficiency virus (HIV), hepatitis B surface antigen (HBsAg), or hepatitis C virus (HCV).
- 4. Has had an acute illness (e.g., upper respiratory infection, viral infection) requiring treatment within 14 days prior to Test Visit 1.

Page 41 CA22747_PROTOCOL AMENDMENT 3_24MAR2020

- 5. Has a fever (> 100.5°F) at Screening or check-in for Test Visit 1.
- 6. Has a body mass index (BMI) greater than 40.0 kg/m² or less than 18.0 kg/m² at Screening.
- 7. Has a history of drug or alcohol abuse within 24 months of Screening, as determined by the Investigator.
- 8. Has a systolic blood pressure < 90 mmHg or > 150 mmHg, diastolic blood pressure < 40 mmHg or > 95 mmHg, or heart rate < 40 bpm or > 99 bpm at Screening.
- 9. Has a post-bronchodilator forced expiratory volume in 1 second to forced vital capacity (FEV₁:FVC) ratio < 0.7 and FEV₁ < 80% of predicted at Screening.
- 10. Has a post-bronchodilator FEV_1 increase $\geq 12\%$ and ≥ 200 mL from pre- to post-bronchodilator at Screening.
- 11. Is allergic to propylene glycol or glycerin.
- 12. Has an estimated creatinine clearance < 70 mL/minute (using the Cockcroft-Gault equation) at Screening.
- 13. Has a positive urine drug or alcohol breath test at Screening or check-in for Test Visit 1.
- 14. If female, the subject is pregnant, lactating, or intends to become pregnant during the time period from Screening through the duration of the study.
- 15. Has taken medication for depression or asthma within 12 months of check-in for Test Visit 1.
- 16. Has used prescription anti-diabetic medication and/or insulin therapy within 12 months of check-in for Test Visit 1.
- 17. Has used medications known to interact with cytochrome P450 (CYP) 2A6 (including, but not limited to, amiodarone, desipramine, isoniazid, ketoconazole, miconazole, phenobarbital, rifampin, tranylcypromine, methoxsalen) within 3 months prior to check-in for Test Visit 1.
- Has used medications known to impact HDL-C (including, but not limited to, "statins", ezetimibe, fenofibrate, gemfibrozil, niacin) within 3 months prior to check-in for Test Visit 1.
- 19. Has used inhalers to treat any chronic medical condition within 3 months prior to checkin for Test Visit 1.
- 20. Has used nicotine-containing products other than manufactured cigarettes (e.g., e-cigarettes, roll-your-own cigarettes, bidis, snuff, nicotine inhaler, pipe, cigar, chewing tobacco, nicotine patch, nicotine spray, nicotine lozenge, or nicotine gum)

Page 42 CA22747_PROTOCOL AMENDMENT 3_24MAR2020 within 14 days prior to check-in for Test Visit 1.

- 21. Has received any medications or substances (other than tobacco) which interfere with the cyclooxygenase pathway (e.g., anti-inflammatory drugs including aspirin and ibuprofen) within 7 days prior to check-in for Test Visit 1.
- 22. Has used methylene blue within 7 days prior to check-in for Test Visit 1.
- 23. Has used any prescription smoking cessation treatments, including, but not limited to, varenicline (Chantix[®]) or buproprion (Zyban[®]) within 3 months prior to check-in for Test Visit 1.
- 24. Is a self-reported puffer (i.e., adult smokers who draw smoke from the cigarette into the mouth and throat but do not inhale).
- 25. Is postponing a planned smoking quit attempt in order to participate in the study.
- 26. Has donated plasma within 7 days prior to check-in for Test Visit 1.
- 27. Has donated blood or blood products (with the exception of plasma as noted above), had significant blood loss, or received whole blood or a blood product transfusion within 56 days prior to check-in for Test Visit 1.
- 28. Has participated in a previous clinical study for an investigational drug, device, biologic, or tobacco product within 30 days prior to check-in for Test Visit 1.
- 29. Is or has a first-degree relative (e.g., spouse, parent, sibling, child) who is a current or former employee of the tobacco or e-cigarette industry or is a named party or class representative in litigation with the tobacco or e-cigarette industry.
- 30. Is or has a first-degree relative (e.g., spouse, parent, sibling, child) who is a current employee of one of the clinic sites.
- 31. Is or has a first-degree relative (e.g., spouse, parent, sibling, child) who is a current employee of the Sponsor.
- 32. Has previously taken part in (from completion of any baseline measurements), has been withdrawn from, or has completed this study.
- 33. Has previously been diagnosed with any form of cancer, except for basal cell or squamous epithelial carcinomas of the skin that have been resected at least 1 year prior to Screening 1.
- 34. In the opinion of the Investigator, the subject should not participate in this study.

4.3 Study Restrictions

4.3.1 Food, Beverages, and Activity

Subjects will be advised of the following study restrictions.

- Alcohol should be avoided for 48 hours prior to Screening and Test Visits 1, 3, and 5.
- Foods containing poppy seeds should be avoided for 48 hours prior to Screening and Test Visit 1 to avoid exclusion for a positive urine drug test.
- Subjects randomized to the *my*blu[™] and continue-smoking arms will be advised to avoid eggplant, meats cooked at high temperatures (e.g., barbecued, grilled, or panfried), cured sandwich meats, bacon, salami, and sausages for 2 days prior to Test Visits 1, 3, and 5 and during confinement.
- Strenuous physical activity which could cause muscle aches or injury, including contact sports should be avoided for 48 hours prior to Screening and Test Visits 1, 3, and 5 and during confinement.
- Donation of blood or blood products, other than for the purpose of this study, should be avoided from Screening through Test Visit 5.

Subjects will be asked to report violations of this advice.

Exceptions of the above study restrictions may be permitted at the discretion of the Investigator and will be documented.

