4.3.2 Medications

Medication use will be assessed to satisfy the inclusion and exclusion criteria. All medications (and reasons for their use) taken from 30 days prior to Screening through the Follow-up Period will be recorded. Except for those medications noted in the exclusion criteria, prescription or over-the-counter medications required to treat an Investigator-approved disease or condition are permitted at the discretion of the Investigator. Hormonal contraceptives (e.g., oral, vaginal ring, transdermal patch, implant, injection) and hormonal replacement therapy are permitted. Use of over-the-counter analgesics (e.g., acetaminophen), antihistamines, nasal decongestants, and dietary supplements are permitted.

Use of anti-inflammatory medications (e.g., ibuprofen) and methylene blue should be avoided for 7 days prior Test Visits 1, 3, and 5 as these medications may interfere with biomarkers being assessed. Decisions to use other concomitant medications (including, but not limited to, those known to impact HDL-C or to interact with CYP2A6; taken for depression, asthma, chronic obstructive pulmonary disease, or diabetes; smoking cessation and nicotine replacement therapy products; or inhalers) during the study will be made in the best interest of the health of the subject. If other drug therapy is required, a joint decision will be made by the Investigator and Sponsor to continue or discontinue the subject. Exceptions may be permitted at the discretion of the Investigator in consultation with the Sponsor (or Sponsor designee), providing the medication in question would have no impact on the study. Any exceptions will be documented and required medications that might impact study endpoints should be considered during interpretation of the study results.

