Following discharge from Test Visit 1, subjects in the *my*bluTM and continue-smoking arms will follow the product use requirements of their randomization arm and will report product use daily. All subjects in the *my*bluTM and continue-smoking arms will be required to present to the clinic site on Day 14 and Day 28 (each ± 2 days) for Test Visits 2 and 3, respectively. Reminder phone calls will be made to the subjects 24 to 48 hours prior to each test visit. Test Visit 2 will be ambulatory and primarily for the return and dispensing of test products for the *my*bluTM arm and for compliance and safety checks for both study arms. Test Visit 3 will be for these purposes in addition to completion of the endpoint assessments during confinement. At the discretion of the site, Test Visit 3 (i.e., Days 28 and 29) may be ambulatory and selected procedures may be performed by subjects at home (e.g., 24-hour urine collection, completion of questionnaires). Subjects will be provided the materials required to complete the selected procedures and will be instructed on at-home procedures (e.g., urine collection method, questionnaires).

Time	Procedures	Comments
	Document AEs and medications	
	Urine sample for cotinine and pregnancy (females) tests	Female subjects must have a negative pregnancy test prior to product dispensing
	Exhaled CO measurement	Exhaled CO should be measured within 1 hour of check-in.
	Document non-compliant tobacco product use and update usual brand cigarette documentation	
	Review of tobacco and nicotine restrictions	
	Test product collection/dispensing	
	Subject product use reporting confirmation	

Table 6Test Visit 2 Schedule

Table 7Test Visit 3 Schedule

Time*	Procedures	Comments
Day 28		
	Check-in events	
	my blu™ product return and combustible cigarette check-in	
	Urine collection for urinalysis, cotinine, and pregnancy (females) tests	Female subjects must have a negative pregnancy test prior to completing the remaining assessments.
	Exhaled CO measurement	Exhaled CO should be measured within 1 hour of check-in.
	Vital signs	Subjects must be seated for at least 5 minutes prior to measurement, must be collected at least 15 minutes after the last study product used.
	Document non-compliant tobacco product use and update usual brand cigarette documentation	
	Update AEs and medications	Throughout the day
	Symptom-driven physical examination	

Time*	Procedures	Comments
	Body weight documentation	

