Following discharge from Test Visit 3, subjects in the *my*blu[™] and continue-smoking arms will follow the product use requirements of their randomization arm and will report product use daily. All subjects in the mybluTM and continue-smoking arms will be required to present to the clinic site on Day 42 and Day 56 (each ± 2 days) for Test Visits 4 and 5, respectively. Reminder phone calls will be made to the subjects 24 to 48 hours prior to each test visit. Test Visit 4 will be ambulatory and primarily for the return and dispensing of test products for the *my*blu[™] arm and for compliance and safety checks for both study arms. Test Visit 5 will be for these purposes in addition to completion of the endpoint assessments during confinement. Subjects will be discharged from the clinical portion of the study at the end of Test Visit 5. At the discretion of the site, Test Visit 5 (i.e., Days 56 and 57) may be ambulatory and selected procedures may be performed by subjects at home (e.g., 24-hour urine collection, completion of questionnaires). Subjects will be provided the materials required to complete the selected procedures and will be instructed on at-home procedures (e.g., urine collection method, questionnaires).

I able 8	rest visit 4 Schedule	
Time	Procedures	Comments
	Document AEs and medications	
	Urine sample for cotinine and pregnancy (females) tests	Female subjects must have a negative pregnancy test prior to product dispensing
	Exhaled CO measurement	Exhaled CO should be measured within 1 hour of check-in.
	Document non-compliant tobacco product use and update usual brand cigarette documentation	
	Review of tobacco and nicotine restrictions	
	Test product collection/dispensing	
	Subject product use reporting confirmation	

Table 8 Test	Visit 4	Schedule
--------------	---------	----------

Table 9	Test Visit 5 Schedule	
Time*	Procedures	Comments
Day 56		
	Check-in events	
	my blu [™] product return and combustible cigarette check-in	
	Urine collection for urinalysis, cotinine, and pregnancy (females) tests	Female subjects must have a negative pregnancy test prior

Time*	Procedures	Comments
		to completing the remaining assessments.
	Exhaled CO measurement	Exhaled CO should be measured within 1 hour of check-in.
	Vital signs	Subjects must be seated for at least 5 minutes prior to measurement, must be collected at least 15 minutes after the last study product used.

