6.4.2 Urine

24-hour urine collections for biomarker measurements will take place during Test Visits 1, 3, and 5. Each 24-hour urine collection will begin at a time following check-in and will end at the same time \pm 30 minutes the following day.

Subjects will be instructed as to urine collection methods. Subjects will be instructed to attempt to void prior to the beginning and at the end of each interval. All urine must be collected during the entire 24-hour interval. The start and stop time of each 24-hour interval and the total weight of the collection will be documented. The weight of the 24-hour urine collection containers will be documented prior to the collection (tare weight) and following completion of the collection.

Urine will be refrigerated during the collection interval. Collections for each subject will be pooled periodically into one labeled container throughout the interval and the total weight (g) will be measured and recorded at the end of the 24-hour interval. Any missed voids will be documented, including the reason for missing. Aliquots will be prepared as noted in the following chart.

At the discretion of the site, 24-hour urine collection during Test Visits 3 and/or 5 may be completed by subjects at home. Subjects will be provided the materials required and will be instructed on the at-home urine collection method.

Page 68 CA22747_PROTOCOL AMENDMENT 3_24MAR2020

Biomarker	Number of Aliquots/ Volume Required	Container Type
Nicotine equivalents	2 aliquots of 5 mL each	polypropylene
1-OHP		
8-epi- PGF2α		
11-DHTXB2		
Creatinine (for adjustment)		
NNAL / NNN	2 aliquots of 10 mL each	UV shielded
MHBMA	_	polypropylene
3-HPMA / CEMA / HMPMA		
S-PMA		
HEMA		
1-AN / 2-AN		
o-tol		
3-OH-B[a]P		
Bio-banking	2 aliquots of 300 mL each	polypropylene

All aliquots will be prepared within 120 minutes from end of the collection and will be stored at $-20 \pm 10^{\circ}$ C until shipped for analysis.

Detailed instructions for collection, processing, and shipping of urine samples will be provided separately.

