6.8 Other Clinical Considerations

6.8.1 Meals

Meals and snacks will be served at appropriate times during confinement as determined by the clinic, taking into account fasting requirements for endpoint assessments. In addition, subjects will fast for at least 1 hour prior to and 1 hour after the start of each PK product use session. Low-mutagen meals (e.g., no meats cooked at high temperatures [barbecued, grilled, or pan-fried], cured sandwich meats, smoked meats, bacon, salami, and sausages) should be served on days with urine collections for biomarkers. Eggplant is also not to be served during the confinement periods. Subjects will not be allowed to use study products during meals.

Water will be provided as desired during the study, and subjects will be encouraged to maintain their usual hydration habits. Up to one caffeinated beverage per meal may be served.

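### The diet restriction was not extended to the 24-hour urine collections that Amendment 3 allows at home on Days 28-29 and 56-57

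*Protocol*

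**What the plan says.** Diet is controlled in two places in the protocol. Section 4.3.1 advises subjects in the myblu and continue-smoking arms to avoid eggplant, meats cooked at high temperature and cured or processed meats "for 2 days prior to Test Visits 1, 3, and 5 and during confinement", and asks them to report violations. Section 6.8.1, which deals with meals provided in confinement, says that low-mutagen meals "should be served on days with urine collections for biomarkers" and that eggplant is not served in the confinement periods.

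The collection rules now go further than confinement. Section 6.4.2 states: "At the discretion of the site, 24-hour urine collection during Test Visits 3 and/or 5 may be completed by subjects at home". Section 6.1.2 says "At the discretion of the site, Test Visit 3 (i.e., Days 28 and 29) may be ambulatory", and 6.1.3 says "At the discretion of the site, Test Visit 5 (i.e., Days 56 and 57) may be ambulatory". Footnote 14 to Table 2 attaches the same option to the confinement marks for these visits. Both sections say that subjects "will be instructed on at-home procedures (e.g., urine collection method, questionnaires"). Notes to Tables 7 and 9 ask home collectors to keep as close as possible to the scheduled times.

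The analysis variable for the urine markers is change from baseline in 24-hour mass excreted (Protocol 7.4.2, SAP 6.2.3). SAP Section 3 still describes the endpoint assessments at Test Visits 3 and 5 as taking place in confinement.

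**The concern.** The protocol restricts diet so that it does not disturb the biomarker results. For a home collection, the stated restriction ends just before the 24 hours in which the sample is produced. A subject who follows 4.3.1 to the letter may eat any listed food during that time. Because this breaks no stated rule, it need not be reported under 4.3.1 and would not obviously lead to exclusion under the per-protocol criteria in 7.2.3.

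Each post-baseline home sample is compared with a baseline sample taken under dietary advice and clinic meals. At stake is the comparability of the two ends of the change-from-baseline value. If home collection is equally common in the arms, the likely cost is extra variability in the between-arm comparison. If it is more common in one arm, part of the between-arm difference may reflect diet. The SAP plans no analysis by place of collection, and its per-protocol analyses of biomarkers cover only the primary BoE (SAP 4.1.3).

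**Working it through.** **Step 1. Setting the passages side by side.** The scheduled collection starts at 14:00-15:00 on Day 28 or Day 56 and ends at about the same time the next day (Tables 7 and 9).

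| | Baseline, Day -2 to -1 | Post-baseline, in clinic | Post-baseline, at home |
|---|---|---|---|
| 2 days before the visit (4.3.1) | covered | covered | covered |
| The 24 hours of collection (4.3.1) | covered, as confinement | covered, as confinement | not covered |
| Meals on collection days (6.8.1) | low-mutagen meals should be served | same | no clinic meals |
| Eating a listed food departs from 4.3.1 | yes | yes | no |

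Baseline has no home option, so the last column exists only after baseline.

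**Step 2. Does another passage close the gap?** The Amendment 3 entry in the revision history lists Table 2 footnote 14 and Sections 6.1.2, 6.1.3, 6.4.2 and 6.6 as updated for home procedures. Sections 4.3.1 and 6.8.1 are not listed, and their current text does not mention home collection. Nor does the diet list appear in 6.1.2, 6.1.3 or 6.4.2.

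**Step 3. Form of the possible shift.** Let f be the share of an arm's collections made at home, and d the mean amount that uncontrolled diet adds to the marker, as a percentage of baseline. The within-arm change shifts by f x d. The between-arm difference shifts by (f_myblu - f_control) x d and is zero when the shares are equal. The documents give neither f nor d. Two sets of assumed values show only the scale:

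- Home collection by 15 of the 175 myblu subjects and by no controls: 15/175 = 8.6%. With d from 5% to 20%, the shift is 0.086 x 5 = 0.4 to 0.086 x 20 = 1.7 percentage points.
- A 30-point difference in share: 0.30 x 5 = 1.5 to 0.30 x 20 = 6 points.

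The planned effect is a 50% reduction (Protocol 7.1).

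**Step 4. Possible cost of noise, using S-PMA as the least powered primary marker.** Inputs from 7.1 are baseline 3348 ng, change SDs 2370 and 1512, 29 per group and one-sided alpha 0.0125. The difference is 0.5 x 3348 = 1674. The standard error is sqrt((2370² + 1512²)/29) = 522, and the ratio is 3.21. A noncentral t with Satterthwaite degrees of freedom (about 47.6) gives power 0.8106, which is the plan's figure. If both SDs rose by 5%, 10% or 20%, power would be 0.77, 0.72 or 0.64. For 3-HPMA it would be 0.99, 0.99 or 0.97. These inflations are assumptions; nothing in the documents says that the listed foods change either marker.

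**The case against.** Several points on the other side are sound.

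- The home instructions are introduced by an e.g., and 6.4.2 says that detailed urine instructions are provided separately. Those may well cover diet. A reader might infer that home collectors are told nothing about food, but the documents do not support that. They show only that the protocol does not require it.
- Baseline diet is not guaranteed either. Section 4.3.1 is advice with exceptions at the investigator's discretion, and 6.8.1 says only what should be served.
- No effect on a primary endpoint is shown. COHb is measured in blood, 6.3.3 describes NNAL as tobacco-specific, and no passage says which markers the listed foods affect.
- If the foods raise a marker, more home collection in the myblu arm makes the reduction look smaller. That is conservative for the one-sided hypothesis. A false positive from this source would need more home collection among controls, and the documents give no reason to expect that.

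A reader might also infer that the arms differ in home collection, because Amendment 3 added 15 subjects to the myblu arm only. The documents give neither enrolment dates nor home-collection counts, so this remains conjecture.

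Finally, the anti-inflammatory window looks like a parallel gap, since those drugs "should be avoided for 7 days prior Test Visits 1, 3, and 5 as these medications may interfere with biomarkers being assessed". It is not one. The window stops at the visit for all three visits, including baseline and in-clinic collections, so home collection creates no new asymmetry. Medications are recorded through follow-up, and 4.3.2 asks that those which might affect endpoints be considered in interpretation.

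These points limit the size of the concern. They do not close the gap between 4.3.1 and 6.8.1 on one side and 6.4.2 on the other.

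**Conclusion.** The gap is real on the current text. The protocol controls diet for in-clinic collections and does not require it during a home collection, although the home sample is compared with an in-clinic baseline. The possible consequences are added noise in the urine change-from-baseline values, or bias if the home share differs between arms. The direction stated for the myblu arm assumes that the listed foods raise the marker.

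The size cannot be determined. It depends on the home share, the dietary effect and the markers affected, none of which the documents give. The documents therefore do not show that any primary result is biased. This is a cheap improvement, not a threat to the primary conclusion.

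**What to change.** In 4.3.1, keep the reference to confinement and add: *and throughout each 24-hour urine collection, wherever it is made*. The confinement wording has to stay because myblu subjects in the PK sub-study have a second in-clinic collection on Days 3-4, and in 4.3.1 only confinement covers Days 1-2 before it. Align 6.8.1 with this wording, and add the food list to the home instructions in 6.1.2, 6.1.3 and 6.4.2.

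When the urine is handed in, record the place of collection and any dietary departures. Add to the SAP a sensitivity analysis of the urine markers by place of collection, and bring the description of Test Visits 3 and 5 in SAP Section 3 into line with the amended protocol. If collections are already complete, recording the place and running the sensitivity analysis may still be possible.

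The cost is about one more day of dietary advice for home collectors, one or two items on the collection record and a small extra analysis.
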